6.4 Data Sources

Responses to the HCP Survey comprised of closed-ended questions or statements with multiple response choices (i.e., questions or statements asking the HCPs to choose from a defined list of responses) and HCP information contained in the sampling frame are the source of the study data.

Screening questions:

- Prescribed Humulin® R U-500 KwikPen® product
- Aware of having received DHCP letter
- HCPs or their immediate family members are not current or past employees of Lilly, Covance, SA, or the FDA
- Didn't previously participate in the survey
- Agree to participate

Data on demographic characteristics:

- Age group
- Gender
- Role at facility
- Facility type
- State or territory of practice
- HCP medical specialty (e.g., General Internal Medicine, Endocrinology/Diabetology, Family Medicine, and Other)

- Number of years practicing medicine/nursing (e.g., <5 years, 5-10 years, 11-15 years, and >15 years)
- Number of Humulin[®] R U-500 KwikPen[®]-treated patients the HCPs prescribed to or managed in the 12 month period preceding the survey (self-reported). Response options are categorical in nature, e.g., 1-5 patients, 6-10 patients, 11-20 patients, and >20 patients.

Data pertaining to evaluation of the effectiveness of the risk minimization measures:

The survey includes questions/statements that will assess HCP understanding about the risks and associated behavior of the HCPs to minimize these risks. The understanding level and behaviors will be analyzed using descriptive statistics and confidence intervals (CIs) and will be used to determine the effectiveness of the risk minimization measures:

- Awareness of the DHCP letter on the correct use of Humulin[®] R U-500 KwikPen[®]
- Understanding of the key safety messages
- Self-reported practices and intentions with respect to communication of the key safety messages in clinical practice

The RMiP will be considered effective if the majority of HCPs demonstrate they are aware of the key safety messages communicated for Humulin[®] R U-500 KwikPen[®].

6.5 Study Size

A sample size of 200 HCPs will provide a confidence interval of ± 5.49 percentage points at the 95% confidence level if 80% of the HCPs answered the key risk questions correctly, as shown in Table 1.

The confidence interval for the percent correct response is calculated using the finite population correction factor as: $p\pm1.96[\sqrt{(p(1-p))}/\sqrt{n}]*\sqrt{(N-n)}/(N-1)$ where p is the proportion of HCPs answering the survey question correctly, N is the population size, and n is sample size.

Table 1: Table of Confidence Intervals by Sample Size and % Answering the Question Correctly

-95% Confidence Level-

	Percent Answering the Question Correctly				
Sample Size	50% 60% 70% 80% 90%				
50	±13.83	±13.55	±12.67	±11.06	±8.30
100	± 9.75	± 9.55	± 8.94	± 7.80	± 5.85
150	± 7.94	± 7.78	± 7.28	± 6.35	± 4.77
200	±6.86	± 6.72	± 6.29	±5.49	± 4.12
250	±6.12	± 6.00	± 5.61	± 4.90	± 3.67

Note: These calculations were performed assuming a population size of 10,000. The confidence intervals are not greatly altered with varying population size assumptions.

Additional measures will assess review and understanding of the RMiP, but these measures do not drive the sample size calculation.

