6.2.1 Population

The initial population in scope for selection consists of the 15,179 HCPs who were sent a DHCP letter and prescribe the Humulin[®] R U-500 KwikPen[®] within 12 months of the launch date. The sampling frame is limited to the 10,442 HCPs (69%) who have a valid email, as recruitment will be implemented via email only.

Initially 1,000 HCPs will be randomly selected in order to obtain 200 completed surveys with a target response rate of 20%. The response rate will be monitored throughout the data collection period of 3-5 months. Of the 1000 initially sent, if any are undeliverable, they will be replaced.

Follow-up via phone or email or randomly selecting additional HCPs will be assessed as options to obtain 200 completed surveys if the initial response rate is lower than 20%. If the response rate is higher than 20% then no follow-up or additional HCP sample will be required.

HCPs who complete the screener and qualify for the survey are included in the survey's analysis population. Data collected on the screener and on the survey will be available for this analysis population.

HCPs who complete the screener, but do not qualify to participate in the survey are included in the screen failures analysis. These HCPs may fail the screener because they indicate that they have not met one of the inclusion/exclusion criteria. Data collected on the screener will be available for this population.

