6.7.4 Primary Objectives and Endpoints

Frequencies and percentages, along with 95% CIs will be used to assess HCP retention and comprehension of the risks associated with the Humulin® R U-500 KwikPen®. The denominator will be the number of HCPs who complete the survey. Specifically, primary endpoints are the proportion of those correctly answering each of the following statements. Response options are either True/False or multiple choice.

- It is appropriate to prescribe Humulin[®] R U-500 KwikPen[®] to patients needing more than 200 units of insulin per day.
- It is important to clearly specify the units of insulin (5-unit increments) on the prescription when prescribing Humulin® R U-500 KwikPen®
- When prescribing Humulin[®] R U-500 KwikPen[®] it is important to inform patients of their dose in units of insulin.
- When administering the Humulin[®] R U-500 KwikPen[®], patients do not need to convert the dose since the dose window shows the number of units to be injected.
- It is important to instruct your patients that they should always have a backup Humulin[®] R U-500 KwikPen[®] available.
- It is important to instruct your patients to not count clicks to audibly verify the correct dose.
- In the event of a Humulin[®] R U-500 KwikPen[®] malfunction, it is appropriate for patients to use a backup pen, call their healthcare provider or pharmacist, or call the Lilly Answer Center; but it is not appropriate to use a syringe to withdraw insulin from the injector.

The RMiP will be considered effective if the majority of HCPs demonstrate they are aware of the key safety messages communicated for Humulin[®] R U-500 KwikPen[®] by correctly answering these statements.

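### The only confidence interval the protocol specifies for percent correct is a Wald interval, which is too short if nearly all HCPs answer an item correctly

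*Protocol*

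**What the plan says.** Protocol Section 6.5 (Study Size) states: "The confidence interval for the percent correct response is calculated using the finite population correction factor as" p plus or minus 1.96 times the binomial standard error times a correction factor. There p is the proportion answering the survey question correctly, n the sample size and N the population size. The planning statement is "A sample size of 200 HCPs will provide a confidence interval of ± 5.49 percentage points at the 95% confidence level"; it assumes a rate of 80% correct. Table 1 runs from 50% to 90% correct, and its note says "These calculations were performed assuming a population size of 10,000". Section 6.2.1 puts the actual frame close to that: "The sampling frame is limited to the 10,442 HCPs (69%) who have a valid email".

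Section 6.7 asks for 95% CIs on all questions that address the objectives. Section 6.7.4 makes percent correct on each item the primary endpoint: "Frequencies and percentages, along with 95% CIs will be used to assess HCP retention and comprehension of the risks". Neither section names an interval method. The effectiveness rule in Sections 6.4 and 6.7.4 is that a majority show awareness of the messages; it is not tied to a confidence limit.

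**The concern.** Section 6.5 describes its formula as the way the interval for percent correct is obtained, and that proportion is the primary endpoint. With no other method named, a programmer working from the protocol would apply this formula to the reported results.

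A Wald interval takes its width from the observed proportion. As that nears 100% the width shrinks to zero, the limits stay symmetric when the sampling distribution is not, and the upper limit can pass 100%.

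Three features of the protocol make results in that range possible. All six true/false items are keyed True (Appendix III). Respondents must have prescribed the pen. They must also recall receiving the letter (Appendix II, screener questions 11 and 14). Table 1 ends at 90%, so the planning grid does not reach the range where the formula fails. At stake is the accuracy of the error bars on the primary results.

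**Working it through.** **Inputs.** n = 200 (Sections 6.2.1 and 6.5), multiplier 1.96, N = 10,000 (note to Table 1), p = 0.80 for planning (Section 6.5).

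**Step 1: reproduce the plan's figure.** Half-width = 1.96 × √(p(1−p)/n) × √((N−n)/(N−1)).

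- 1.96 × √(0.80 × 0.20/200) = 5.544 points.
- √(9,800/9,999) = 0.9900.
- 5.544 × 0.9900 = 5.488, which rounds to the stated ±5.49.

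The same formula reproduces all 25 cells of Table 1 to two decimals. With the frame of 10,442 it again gives ±5.49, and with 15,179 it gives ±5.51, so the note that population size matters little also holds.

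**Step 2: notation.** In the text available here, the root in the correction factor covers N−n only. Taken literally, the factor is √9,800/9,999 = 0.0099, which would give ±0.055 points and match no cell. Step 1 shows which form was used to build the table.

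**Step 3: limits near 100%, n = 200.** Wald with the correction, N = 10,000; Wilson without correction:

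| Correct | Wald (%) | Wilson (%) |
|---|---|---|
| 160/200 | 74.5 to 85.5 | 73.9 to 85.0 |
| 196/200 | 96.1 to 99.9 | 95.0 to 99.2 |
| 197/200 | 96.8 to 100.2 | 95.7 to 99.5 |
| 198/200 | 97.6 to 100.4 | 96.4 to 99.7 |
| 199/200 | 98.5 to 100.5 | 97.2 to 99.9 |
| 200/200 | 100 to 100 | 98.1 to 100 |

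For example, 198/200: 1.96 × √(0.99 × 0.01/200) × 0.9900 = 1.365 points, so 99.0 ± 1.4.

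**Step 4: actual coverage.** For each true proportion, add the hypergeometric probabilities (N = 10,000, n = 200) of the counts whose interval contains the truth:

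| True % correct | Wald | Wilson | Clopper-Pearson |
|---|---|---|---|
| 80 | 94.4% | 96.1% | 96.1% |
| 90 | 93.0% | 95.8% | 96.9% |
| 95 | 92.8% | 96.9% | 96.9% |
| 97 | 93.5% | 94.6% | 96.7% |
| 98 | 90.6% | 93.6% | 96.4% |
| 99 | 86.8% | 95.0% | 98.5% |
| 99.5 | 63.6% | 92.2% | 98.3% |

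The Wald misses are mostly on the favourable side. At a true 98% the lower limit lies above the truth in 8.7% of samples, and at 99% in 13.1%, against a nominal 2.5%. The 13.1% is exactly the chance of 200/200, where the interval has zero width.

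**Step 5: the effectiveness rule.** At a true 50%, Wald and Wilson coverage are the same, 0.9465. Near 100%, every interval lies far above a majority.

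**The case against.** The strongest objection is that the formula sits under Study Size, beside a precision table, and that the choice among Wald, Wilson and exact limits is commonly left to a statistical analysis plan, which is not at hand. This stands in part: a later plan may name another method. But Section 6.5 does not leave the point open. It states how the interval for percent correct is computed, and a different method in a later document would conflict with it unless the protocol marks its formula as planning only.

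Second, the ceiling is not forecast. The protocol plans on 80%, where Wald coverage is 94.4%. An answer of not knowing counts as incorrect, and the malfunction item is a select-all question with one unsafe option. This stands: results near 100% are a possibility drawn from the answer key and the screening, not an expectation in the document.

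Third, the differences in reported limits are small, about 1 to 2 points at the lower end, and Wilson also dips below 95% in places. Both are true. The 63.6% at a true 99.5% is an extreme case driven by samples with no wrong answer.

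A reader might also infer from the literal root that the study's precision is overstated 100-fold. The documents do not support this. Every figure in Table 1 is right, no stated figure is too narrow, and the scope of the root may have been lost when the PDF was read by a program.

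**Conclusion.** The concern holds as a limited point about the reported primary intervals. Under simple random sampling with n = 200 and N = 10,000, the one interval the protocol specifies covers 92.8%, 90.6% and 86.8% at true values of 95%, 98% and 99%. It gives impossible upper limits at 197 to 199 of 200, and it claims certainty at 200/200. This matters only if some items come out near 100% correct.

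A reader might infer that the conclusion on effectiveness is at risk. It is not: the rule is a majority, tied to no confidence limit, and it would be met under any of these intervals wherever Wald fails. The sample size and Table 1 need no change. The correction is worth making because the intervals are themselves a planned primary output and the change costs almost nothing.

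**What to change.** In Sections 6.7 and 6.7.4, state that reported 95% CIs for percent correct are Wilson (or Clopper-Pearson) intervals. In Section 6.5, say that the formula and Table 1 serve planning only.

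The cost is one sentence in each place and one option in the SAS program. The small downside is asymmetric or slightly wider limits: at the planned 160/200, Wilson gives 73.9 to 85.0 (width 11.0) against Wald 74.5 to 85.5 (width 11.0), so planned precision is essentially unchanged. Clopper-Pearson is somewhat wider (73.8 to 85.3) and errs towards over-coverage.

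Dropping the finite population correction from the reported intervals is optional, since at 80% correct it moves the half-width only from ±5.49 to ±5.54.

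As a minor notation point, check the original page of Section 6.5 and, if needed, write the factor with the root over the whole ratio (N−n)/(N−1).

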6.6 Data Management

All data collected during the survey will be held confidentially by SA. They will program and host the survey. The survey data will be transferred from SA to Covance via a secure method and stored on the secure SAS server within the study area. Covance's data transfer standard operating procedures (SOPs) will be followed. Only study staff who need the data to complete the analysis will be granted access. No identifiable information will be required from any HCP, but will be collected if they are eligible and wish to receive payment.

The survey is programmed to ensure the HCP cannot skip ahead and will only allow for missing data when caused by skip patterns. Skip logic as well as the ability to mark only one response or multiple responses are part of the programming for the survey administration and minimize the occurrence of data entry errors. There will be no queries to HCPs for this project. Datasets and analytic programs will be kept on the secure Covance SAS server. All statistical programs will be developed using SAS® Version 9 (or later) software.

6.7 Data Analysis

Evaluation of the effectiveness of the DHCP letter in conveying key safety information for the Humulin® R U-500 KwikPen® will be primarily descriptive in nature. Frequency distributions with 95% CIs will be calculated for responses to all questions that address the survey objectives. Responses to each question relating to the key safety messages will be categorized as "Correct response" and "Incorrect response". Additionally, "I don't know" is categorized as an incorrect response unless otherwise specified.

The following sections will be reported as part of the analysis.

6.7.1 Analysis Data Sets

The Analysis Set will consist of all eligible HCPs who undertake the survey. The Analysis Set will be used to assess all the study objectives unless otherwise stated.

The Screening Set will consist of all HCPs identified as being ineligible for reasons other than immediate refusal to participate or prior participation. Demographic information will be presented for the Screening Set.

6.7.2 Survey Administration Statistics

Survey administration statistics will be reported. This summary will include the number of:

- Survey invitations issued by and specialty
- Survey invitations returned due to incorrect email address
- HCPs who responded to the invitation to participate in the survey
- Ineligible HCPs along with the reasons for ineligibility
- HCPs eligible for participation in the survey
- Eligible HCPs who completed the survey

These values will be summarized with the counts and percentage of HCPs. The percentage will be based on the number of HCPs in previous categories which will be detailed in the table shells. For example, the percentage of ineligible and eligible HCPs will be based on the number of HCPs responding to the survey.

6.7.3 Demographic and Other Baseline Characteristics

Demographic variables will be summarized for all HCPs, the Analysis Set and the Screening Set. These will include the distribution of HCPs by:

- Age groups
- Gender
- Practice setting
- State/region
- Medical specialty
- Years in medical practice
- Number of patients treated with Humulin[®] R U-500 KwikPen[®].

These categorical variables will be summarized with frequencies and percentages.

6.7.4 Primary Objectives and Endpoints

Frequencies and percentages, along with 95% CIs will be used to assess HCP retention and comprehension of the risks associated with the Humulin® R U-500 KwikPen®. The denominator will be the number of HCPs who complete the survey. Specifically, primary endpoints are the proportion of those correctly answering each of the following statements. Response options are either True/False or multiple choice.

- It is appropriate to prescribe Humulin[®] R U-500 KwikPen[®] to patients needing more than 200 units of insulin per day.
- It is important to clearly specify the units of insulin (5-unit increments) on the prescription when prescribing Humulin® R U-500 KwikPen®
- When prescribing Humulin[®] R U-500 KwikPen[®] it is important to inform patients of their dose in units of insulin.
- When administering the Humulin[®] R U-500 KwikPen[®], patients do not need to convert the dose since the dose window shows the number of units to be injected.
- It is important to instruct your patients that they should always have a backup Humulin[®] R U-500 KwikPen[®] available.
- It is important to instruct your patients to not count clicks to audibly verify the correct dose.
- In the event of a Humulin[®] R U-500 KwikPen[®] malfunction, it is appropriate for patients to use a backup pen, call their healthcare provider or pharmacist, or call the Lilly Answer Center; but it is not appropriate to use a syringe to withdraw insulin from the injector.

The RMiP will be considered effective if the majority of HCPs demonstrate they are aware of the key safety messages communicated for Humulin[®] R U-500 KwikPen[®] by correctly answering these statements.

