The research questions motivating this study relate to how well the distribution of the DHCP letter has proceeded in the early post-launch period and how well that communication material conveys the most significant risks of Humulin[®] R U-500 KwikPen[®] to prescribers. The study also evaluates prescriber understanding about important patient education about those risks. As noted above, this early evaluation focuses on process measures related to reaction, learning, and planned behavior.

The primary study objective is to evaluate the impact of the DHCP letter on prescriber understanding about the risk of hypoglycemia and educational points to be emphasized in discussion with patients.

Retention and comprehension by HCPs of the following specific key safety messages will be tested in line with this objective. Specifically, HCPs should:

- only consider prescribing Humulin[®] R U-500 KwikPen[®] to patients needing more than 200 units of insulin per day.
- specify the prescribed dose in units of insulin (5-unit increments) on the prescription.
- inform patients of their dose in units of insulin.
- educate patients that no dose conversion is needed with Humulin[®] R U-500 KwikPen[®] and that the dose window shows the number of units to be injected.
- educate patients not to withdraw Humulin[®] R U-500 insulin from the KwikPen[®] with a syringe.
- instruct patients to maintain backup Humulin® R U-500 KwikPen®.
- instruct patients in the event of a malfunction, to use their backup pen or contact a pharmacist, healthcare professional, or The Lilly Answers Center for more information at [name].
- teach patients not to count clicks to determine their dose when using Humulin[®] R U-500 KwikPen[®].

The secondary objectives include

- assessing the proportion of HCPs receiving and reading the DHCP letter and their reactions to the risk mitigation communication content.
- querying prescriber intentions regarding patient education around safe use of the Humulin[®] R U-500 KwikPen[®].

6 Research Method

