6.1 Study design

This is a cross-sectional survey to be conducted in the United States. Eligible HCPs will have received the DHCP letter in April 2016 and subsequently prescribed the Humulin[®] R U-500 KwikPen[®]. The HCPs who received the DHCP letter include endocrinology specialists, primary care physicians, advanced practice registered nurses, nurse practitioners, and physician assistants who have prescribed Humulin[®] U-500 (in vial dosage forms) during the 12 months prior to the Humulin[®] R U-500 KwikPen[®] product launch. A random sample of HCPs will be recruited to participate in the survey from the list of HCPs who received a DHCP letter via email. The HCP survey will be administered online.

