6.2 Setting

The assessment survey will be executed and the analysis completed within approximately 18 months of the product launch.

Eligible HCPs will receive an invitation to participate via email that includes a link to the survey (Appendix II). The invitation will include an overview of the rationale for the survey, information on how to access and complete the survey online, and privacy information. The average survey is expected to take approximately 15 minutes to complete.

The invitation will also indicate that HCPs will be compensated with an incentive card having a \$50 value. All those providing screening information are eligible, with the exception of HCPs who are licensed and practice in Minnesota, Vermont, Massachusetts or the District of Columbia and Advanced Practice Registered Nurses (APRNs) in Connecticut in accordance with state laws. HCPs from these states can elect to participate, although they will not be paid. HCP-identifying information will be utilized for the purposes of providing payment and will be managed by a third party vendor, Schlesinger Associates (SA).

HCPs eligible for compensation, who complete the screening questions, will be mailed their honorarium. Additionally, HCPs will be emailed a letter thanking them for their time and effort. The email will also include a link to the DHCP letter on the correct use of Humulin[®] R U-500 KwikPen[®] and a link to the correct answers to key safety message questions (Appendix III).

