6.8 Quality Control

User Acceptance Testing (UAT) will be performed on the survey using a sample of 8-10 HCPs. The UAT procedure is designed to assess comprehension among HCPs regarding the words and phrases used in select survey questions and response options. UAT will also assess the clarity of the survey questions as presented to HCPs and the interest and acceptance of the surveys among all prospective HCPs and flow and ease of completing the surveys.

Online administration allows for additional randomization of response options, offsetting potential order effects. Questions pertaining to reading and reactions to the DHCP letter are asked after the risk questions. During the course of online administration, the back-button on the survey is disabled preventing alteration of responses once reviewed and entered.

The data are also checked as part of the UAT process to make sure that all of the data collected within the online survey environment are correctly extracted from the system for use in the programming environment.

In addition to the UAT processes for the survey instrument and programming environment, several other strategies will be used to ensure data quality. The randomized sampling strategy outlined above helps ensure representativeness, avoid volunteer bias, and provides an additional means for ensuring valid data. In the analysis, demographic criteria are summarized for those who met survey inclusion criteria against those who did not meet the criteria.

All statistical programs will be developed and validated using good programming practice guidelines. This is a one-time cross-sectional survey with HCPs, there is no risk to any patients, and Institutional Review Board (IRB) approval is not required.

All analyses will be performed using SAS® Version 9 (or later) software. Covance will follow Covance's standard operating procedures in the creation and quality control of all tables, listings, figures and analyses. Lilly or its designee will review all tables, listings, and figures for accuracy.

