6.10 Measures to Minimize Bias

HCPs completing the screener and meeting the Humulin[®] R U-500 KwikPen[®] survey eligibility requirements will be directed to participate in the online survey. Survey biases will be minimized through carefully constructed, non-leading survey questions, and a thorough internal validation process. Online forms will be programmed such that HCPs have access to only one survey question at a time; once a question is submitted, HCPs do not have the option of revisiting it, i.e., the back button is disabled. Lists of response options will be randomized to minimize the potential for positional bias.

Correct responses will be provided to the physicians following recording of their response, allowing for feedback on performance and reinforcing correct information and/or best clinical practice.

7 Protection of Human Subjects

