15. Please answer True, False, or I don't know for each of the following statements regarding Humulin® R U-500 KwikPen®.

		True	False	I don't know
a	It is appropriate to prescribe Humulin® R U-500 KwikPen® to	0	0	0
	patients needing more than 200 units of insulin per day.	1	2	3
b	It is important to clearly specify the units of insulin (5-unit	0	0	0
	increments) on the prescription when prescribing Humulin® R U-	1	2	3
	500 KwikPen [®] .			
c	When prescribing Humulin [®] R U-500 KwikPen [®] it is important to	0	0	0
	inform patients of their dose in units of insulin.	1	2	3
d	When administering the Humulin [®] R U-500 KwikPen [®] , patients do	0	0	0
	not need to convert the dose since the dose window shows the	1	2	3
	number of units to be injected.			
e	It is important to instruct your patients that they should always have	0	0	0
	a backup Humulin [®] R U-500 KwikPen [®] available.	1	2	3
f	It is important to instruct your patients not to count clicks to	0	0	0
	determine their dose.	1	2	3

[PROGRAMMING NOTE: Randomize the list above a-f.]

16. In the event of a Humulin® R U-500 KwikPen® malfunction, what would you instruct patients to do? (please select all that apply)

□ Use a backup pen
□ Use a syringe to withdraw the insulin from the KwikPen®
□ Contact a pharmacist or healthcare professional
□ Contact the Lilly Answer Center for more information at [name]

17. My answers to the true/false statements earlier about the Humulin® R U-500 KwikPen® were based on...(choose all that apply)

□ Professional knowledge about the use of human insulin products.
□ Previous experience with KwikPen® technology in other Lilly products such as Humalog □ Familiarity with the Humulin® R U-500 KwikPen® package insert.
□ Knowledge gained from interaction with Lilly's sale representative.
□ Knowledge gained from the Humulin Dear Health Care Provider letter.

[PROGRAMMING NOTE: Randomize the response options above 1-7.]

Study Protocol for Humulin® R U-500 KwikPen®

₆ □ Guessing

7 □ Online information

labeling.

18. Did you read the Dear Health Care Provider letter provided to you by Eli Lilly and Company on "Important Prescribing Information" for the Humulin® R U-500 KwikPen® (insulin human)?
₁ □ Yes
₂ □ No
3 □ I don't recall
[PROGRAMMING NOTE: If participant answers "1" then go to following items based on
agreement scales. If participant answers "2" or "3" skip the following series of 4 items identified under 19 and go to the following question.]

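### The primary endpoints are meant to reflect retention, but the printed survey items neither ask for unaided answers nor identify look-ups during the survey

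*Protocol*

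**What the plan says.** Section 5 sets the task: "Retention and comprehension by HCPs of the following specific key safety messages will be tested in line with this objective". Section 6.7.4 repeats the pair of terms for the primary endpoints, which "will be used to assess HCP retention and comprehension of the risks associated with the" product. It then calls the risk minimization plan effective if a majority of HCPs show awareness of the messages by answering correctly. The primary objective itself is worded as prescriber understanding.

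On mode, Section 6.1 states: "The HCP survey will be administered online". Section 6.2 describes an emailed invitation whose contents are the rationale plus "information on how to access and complete the survey online, and privacy information".

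The controls on answering are in two places. Section 6.8 says that "the back-button on the survey is disabled preventing alteration of responses once reviewed and entered", that response options are randomized, and that questions on reading the letter come after the risk questions. Section 6.10 adds one question at a time and repeats that "once a question is submitted, HCPs do not have the option of revisiting it, i.e., the back button is disabled".

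In Appendix II, screener Q14 asks whether the HCP is aware of having received the letter. The knowledge items follow at once. The stem of Q15 reads "Please answer True, False, or I don't know for each of the following statements regarding" the product, and Q16 asks what patients would be told to do if the pen malfunctions. Q17 then asks on what the true/false answers were based, with multiple selections allowed. One option is simply "Online information".

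**The concern.** Retention means knowledge the HCP holds when answering. In a self-administered online survey, an HCP who is unsure can consult the letter or the label before submitting an answer, and Q14 has just reminded them that the letter exists. A response obtained that way scores as correct but says nothing about retention.

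The error runs in one direction. The letter and label contain the keyed answers, so consulting them moves responses towards correct and towards the plan being judged effective. The confidence interval covers sampling error only and would not reveal the shift. A separate analysis plan could not repair this afterwards, because the instrument in Appendix II does not collect the information needed.

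**Working it through.** **Step 1: do the documented controls reach look-ups?**

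| Feature | Where | What it addresses | Look-ups? |
|---|---|---|---|
| Randomized response options | 6.8, 6.10 | Order effects | No |
| One question at a time, no going back | 6.8, 6.10 | Revising earlier answers | No; a source can be consulted before submitting |
| Letter-reading questions after the risk items | 6.8 | Cueing | No; Q14 already names the letter |
| Letter and answers linked only in the thank-you email | 6.2, Appendix III | Early disclosure | Partly; the survey does not hand over the answers |
| Q17 source of answers | Appendix II | Self-reported basis | Partly; see step 2 |

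No time limit or item timing is described. Section 6.9 names self-report bias in general, not look-ups.

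**Step 2: what can Q17 show?** The package-insert and letter options are worded as familiarity and knowledge gained, so they read as prior knowledge. The online option is ambiguous as to when the reading took place. No option refers to material consulted while answering. Q17 concerns only the true/false statements, so Q16, the item that contains the syringe-withdrawal choice, is outside it.

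**Step 3: reproduce the plan's precision.** Inputs from Section 6.5: n = 200, N = 10,000.

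Half-width = 1.96 × √(p(1-p)/n) × √((N-n)/(N-1))

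- p = 0.80: 1.96 × √(0.16/200) × √(9800/9999) = 5.49 points, as stated.
- p = 0.60: 1.96 × √(0.24/200) × √(9800/9999) = 6.72 points, as in Table 1.

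**Step 4: size of the shift.** Let p be the share who would answer correctly unaided, and L the share of the rest who look up and then answer correctly. L is not in the documents; 10% to 30% is an assumption.

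Observed = p + L(1-p)

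| True p | L = 10% | L = 20% | L = 30% |
|---|---|---|---|
| 80% (planning value) | 82% | 84% | 86% |
| 60% (assumed) | 64% | 68% | 72% |
| 40% (assumed) | 46% | 52% | 58% |

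At 80% the shift exceeds the stated half-width only if L > 5.49/20 = 27%. At 60%, L = 30% adds 12 points against a half-width of 6.72.

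**Step 5: effect on the majority rule.** Taking majority as above 50%, the rule changes only if p < 0.5 and L > (0.5-p)/(1-p). For p = 0.40 this is 0.10/0.60 = 17%; for p = 0.45 it is 0.05/0.55 = 9%. With p = 0.40, the exact binomial chance of at least 101 of 200 correct on one item is 0.002 with no look-up, and 0.11, 0.69 and 0.99 for L = 10%, 20% and 30%.

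**Step 6: exclude, or count as not correct?** Take p = 0.40 and suppose 40% of the non-knowers look up and all say so. They are 0.60 × 0.40 = 0.24 of the sample.

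- Observed: 0.40 + 0.24 = 64%.
- Excluding them: 0.40/(1-0.24) = 0.40/0.76 = 52.6%, a false majority.
- Counting them as not correct: 40%, the true value.

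If instead 40% of all HCPs look up regardless of knowledge, counting them as not correct gives 0.40 × 0.60 = 24%, below the true value. So this rule does not overstate unaided knowledge in either case, provided look-ups are reported; exclusion can.

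**The case against.** A reader might infer that the plan nowhere asks for unaided answers. The documents do not support that. Appendix II is titled as containing the invitation, and Section 7.1 refers to an introductory message and to survey instructions, but none of these texts is supplied. Section 6.2 only summarizes the invitation, and a request could sit within its information on completing the survey. The absence is established only for the printed screener and items.

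A reader might also infer that retention is the sole construct. It is not: comprehension stands beside it, the objective speaks of understanding and the success rule of awareness. No passages contradict each other on this point, and no stated figure is wrong.

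There are also reasons to expect few look-ups. Payment follows completion of the screener, not correct answers. HCPs are told that their answers do not affect their ability to prescribe. Q15 offers a don't-know choice, and the survey is expected to take about 15 minutes. The letter went out in April 2016, and the copy in Appendix I carries a print mark, so easy online access to it is not shown; for the label, Section 10 gives a web address. At the planning value of 80%, a look-up rate of 10% or 20% stays within the stated margin.

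All of this stands, and it limits what can be said about frequency and size. It leaves in place that the printed items do not discourage looking up, that nothing described would identify it, and that retention is one of the two things the primary endpoints are said to assess.

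**Conclusion.** The point holds as a cheap improvement. Percent correct from this instrument, as printed, does not separate retained knowledge from answers looked up during the survey. Any look-up that yields the keyed answer raises the result by L(1-p): 2 to 6 points at 80% for an assumed L of 10% to 30%, and more at lower p.

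The stronger conclusion, that the effectiveness verdict is unsafe, is not supported. It would need true knowledge below 50% together with enough look-ups, and the documents give no reason to expect the former and no figure for the latter. The conclusion also depends on the unseen invitation and introductory message: if they already ask for unaided answers, the instruction part falls away and the Q17 gap remains.

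**What to change.** Before launch, check the invitation and introductory message. Then:

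- Directly above Q15, and worded to cover Q16, add: *Please answer from what you know now, without consulting the letter, package insert or internet.*
- In Q17, add the option *information I looked up while answering*, reword the online option to *online information read before this survey*, and extend the question to Q16.
- Keep all completers in the denominator of the primary analysis, as Section 6.7.4 has it. Add one supportive table that counts answers from HCPs who report looking up as not correct, labelled as a lower bound. Do not exclude these HCPs.
- Name the issue in Section 6.9.

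The cost is one line of text, one new and one reworded response option, a wider Q17 stem, one table and one sentence. Sample size, recruitment and the primary analysis are unchanged. Percent correct may come out slightly lower. The look-up option is itself self-reported, so the table is a lower bound only to the extent that look-ups are admitted. Because Q17 is answered once per HCP, the table will also discount items that an HCP knew unaided.
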